## A UW Phase II Trial of Multicatheter HDR Brachytherapy Following Lumpectomy for Early Stage Breast Cancer

### SCHEMA

### Systemic Therapy

Cytotoxic chemotherapy should not start until at least two-weeks post-brachytherapy to allow adequate time for healing. Chemotherapy prior to brachytherapy is not permitted. Hormonal therapy may be utilized in any clinically appropriate sequence but will be discontinued during the one-week brachytherapy treatment course.

### ELIGIBILITY:

- Invasive ductal, medullary, papillary, colloid (*mucinous*), tubular histologies or Ductal carcinoma in situ (DCIS)
- Tumor Stage: Tis, T1, T2 if lesion  $\leq$  3 cm
- Nodal Stage: N0 (*negative sentinel node mapping is acceptable*) (subjects with DCIS are exempt from nodal staging)  
*or N1(1-3 nodes positive **and** no extracapsular extension)*. This represents a cohort of patients that would not ordinarily receive axillary irradiation.
- Clearly visible target as defined by ultrasound, surgical clips, or mammography
- Unifocal breast cancer (*single focus which can be encompassed by one lumpectomy*)
- Negative surgical margins
- Negative post-lumpectomy mammogram if cancer presented with malignancy-associated microcalcifications
- No Paget's disease of the nipple or extensive intraductal component (EIC by Harvard definition: 1) more than 25% of the tumor is DCIS and there is DCIS in adjacent breast tissue, or 2) an intraductal carcinoma with microinvasion).
- No previous radiation or chemotherapy for current breast cancer
- No collagen vascular disease (systemic lupus erythematosis, scleroderma, or dermatomyositis)
- No co-existing medical conditions with life expectancy  $<$  2 years.
- Age  $>$  18 years old
- No pregnant or lactating women.
- No psychiatric or addictive disorders which would preclude obtaining informed consent
- Signed study-specific consent form

**ELIGIBILITY CHECK****The following questions will be asked at registration:**

(Y) 1. Does the patient have histologically confirmed invasive ductal, medullary, papillary, colloid (*mucinous*), tubular cancer of the breast, or DCIS

(Y) 2. Is the AJCC T classification Tis, T1-2, N0-1, M0?

(Y) 3. Is the tumor size  $\leq$  3 cm.

(Y) 4. Are there  $\leq$  3 nodes positive without extracapsular extension?

(Y) 5. Does the patient have a well-defined target (ultrasound-defined seroma, surgical clips, or mammography)?

(N) 6. Has the patient undergone lumpectomy resulting in negative tumor margins? (*if yes, skip to Q8*)

(Y) 7. If no, is re-excision planned prior to introduction of radiation sources? (*failure to meet all criteria subsequent to re-excision will result in ineligibility*)

(Y/N) 8. Any evidence of pre-excision breast microcalcifications in the initial mammogram?  
 (Y) If yes, was a postoperative mammogram done and found negative for residual suspicious microcalcifications?

(N) 9. Any evidence of multicentric breast tumor, or unresolved suspicious synchronous tumors/calcifications

(N) 10. Any evidence of Paget's disease of the nipple, tumor involving skin, internal mammary or supraclavicular lymph nodes or distant metastasis?

(N) 11. Any evidence of collagen vascular disease or shortened life expectancy from coexisting medical conditions ( $< 2$  yrs)?

(N) 12. Any prior radiotherapy, chemotherapy or non-hormonal therapy for the present breast cancer?

(N) 13. Is the patient pregnant or lactating?

(Y) 14. Is the patient  $\geq$  18 years old?

## 1.0 **BACKGROUND**

### **Breast Conservation Therapy (BCT)**

BCT is now widely accepted as a treatment option for most women with Stage I and II invasive breast cancer and most patients with ductal carcinoma in situ (DCIS). Six prospective randomized trials have clearly demonstrated similar overall and distant disease-free survival for patients receiving breast-conserving therapy, compared with patients treated by conventional mastectomy. Despite superior cosmetic outcome, BCT is more complex and requires a protracted treatment regimen comprised of 6 weeks of daily external beam radiation therapy to the whole breast. This often proves prohibitive for the working woman, elderly patients, and those who live at a significant distance from a radiation treatment center. In addition, with the more frequent use of adjuvant chemotherapy in both node-negative and node-positive patients, substantial delays can be incurred prior to the initiation of systemic chemotherapy if a conventional fractionated course of irradiation (XRT) is given first or in delivery of loco-regional XRT if chemotherapy is delivered beforehand. Thus, despite the potential benefits, only 30-50% of patients who are candidates for breast conservation actually receive it.

### **A Paradigm Shift from Whole Breast to Partial Breast Irradiation**

Most of the logistical problems associated with BCT relate to the protracted course of external beam XRT delivered to the whole breast. Standard therapy after tumor excision generally includes five weeks of external beam XRT to the whole breast (45-50 Gy) followed by an additional 10-15 Gy boost to the tumor bed. The rationale for this approach is based upon two principles. First, higher doses of XRT are given to the 'tumor bed' in an attempt to control residual small foci of cancer that may be left behind after excision alone. Second, whole breast XRT is used to eliminate possible areas of occult multicentric in situ or infiltrating cancer in remote areas of the breast. That such remote, multicentric areas of cancer exist has long been established. However, the biological significance of these areas of occult cancer is unknown and the necessity to prophylactically treat the entire breast has recently been questioned.

There are at least six prospective randomized trials that have been conducted comparing the outcome of patients treated with lumpectomy alone or followed by whole breast XRT. Across these studies, there is a similar 3-fold reduction in the ipsilateral breast failure rate with the addition of radiotherapy. For instance, in the NSABP B-06 randomized prospective trial, which included patients with invasive cancers up to 4 cm in size with negative surgical margins, the breast recurrence rate of 43% with lumpectomy alone is considerably higher than the 10% breast failure rate of the lumpectomy and whole breast irradiation arm. In these studies, the percentage of patients receiving whole breast irradiation who recur in a remote location of the breast potentially not covered by partial breast irradiation was low (< 3.5%). Is this absence of the expected number of remote breast recurrences due to sterilization of other quadrants by the whole breast radiation therapy employed in these series or to the biological insignificance of occult cancer foci in remote quadrants of the breast? If the former is true, then one would expect increased remote relapses in the conservative surgery alone patients.

To address this question, one must examine patients treated with surgery only and evaluate the number of remote recurrences. In fact, the proportion of patients who recur in a portion of the breast that would not be covered by partial breast irradiation is the same as patients receiving whole breast irradiation. This observation is validated by studies such as those conducted by Liljegren and Crile also demonstrated that 85% and 84% of local recurrences were in the immediate vicinity of the lumpectomy site defined as the surgical scar and the skin directly over the surgical field translating to an absolute risk of remote recurrence of 3.0% and 1.7%, respectively. From these data, one can infer that radiation therapy following lumpectomy has as its maximal effect on the reduction of breast cancer recurrence at or very near the lumpectomy site casting doubt on the belief that remote recurrences originate from multicentric disease at the time of the index lesion demonstrated on histopathology. If the above observations are valid, radiation therapy can be confidently directed to the tissue surrounding the excision cavity of the breast.

### Clinical Experience:

There are currently several groups studying the efficacy of lumpectomy bed irradiation alone in the management of early stage breast cancer patients treated with BCT. Both interstitial brachytherapy techniques as well as external beam irradiation protocols have been implemented. Preliminary results from these trials are very encouraging and the techniques have been shown to be safe, tolerable, and highly reproducible (Data outlined in table below).

Partial breast irradiation experience with >2-year follow-up series with patient selection criteria and quality assurance for brachytherapy							
Author/institution	No. of cases	Follow-up interval (months)	Dose rate/(pt no.)	Scheme	Total dose (Gy)	% Breast recurrence	Good/excellent cosmesis
King et al. Ochsner Clinic New Orleans, Louisiana	52	75	LDR/(26)	>.4 Gy/hr	45	2	75
Vicini et al. William Beaumont Hospital Royal Oak, Michigan	196	65	HDR/(26) LDR/(120) HDR/(79)	4 Gy × 8 .52 Gy/hr 4 Gy × 8 3.4 Gy × 10	32 50 32 34	1.2	91
Krishnan et al. University of Kansas Kansas City, Kansas	24	47	LDR 20–25 Gy	over 24–48 hr	20–25	0	100
Polgar et al. National Institute of Oncology Budapest, Hungary	45	60 †	HDR/(8) HDR/(37) HDR/(64)	4.33 Gy × 7 5.2 Gy × 7 5.2 Gy × 7	30.3 36.4 36.4	4.4	97.8
Cionini et al. University of Florence Florence, Italy	89 ‡	30	Wide-volume electron (25)	2 Gy × 25	50	1.1	not stated
Wazer et al. Tufts University Boston, Massachusetts	90	27	LDR stated	not	50–60	4.4	not stated
Arthur et al. Virginia Commonwealth University Richmond, Virginia	32	33	HDR	3.4 Gy × 10	34	3	88
Lawenda et al. Massachusetts General Hospital Boston, Massachusetts	44	42	HDR/(31) LDR/(13)	3.4 Gy × 10 .50 Gy/hr 50	34 45 50	0	79.6
	48	37	LDR 50 cGy/hr		55 60	0	92

Although these studies require longer follow-up, they have demonstrated that with appropriate patient selection, excellent local control and cosmetic outcome can be achieved with breast brachytherapy with minimal toxicity.

### University of Wisconsin Hospital Experience

From 11/2000 to 4/2004, 240 pts have been treated with high-dose rate accelerated partial breast irradiation at our institution (211 interstitial multiple catheters). Selection criteria have included tumors < 3 cm pathologic size, 0-3 positive nodes with no extracapsular spread, negative margins and negative post-lumpectomy mammography. Two techniques, prone template with digital mammographic-guidance and supine with ultrasound or fluoroscopic guidance were used for catheter placement. Target volume has remained constant as the surgical cavity with 2 cm margin but at least 5-mm deep to the skin surface and no deeper than the pectoral fascia. In 5/2002, CT-based 3-D treatment planning was implemented allowing more accurate target delineation, improved geometric coverage of the target volume, and dosimetric verification. The volume of breast receiving 100% and 150% ( $Vol_{100\%}$ ,  $Vol_{150\%}$ ) of the prescribed dose have been determined from dose volume histograms for each patient. The dose homogeneity index, and percent target volume receiving 100% of the prescription dose was determined for quality assurance. There has been excellent coverage of the target volume with fractionated HDR brachytherapy delivered in the supine position (32-34 Gy/8-10 bid fractions). Interstitial breast brachytherapy has been successfully delivered with high quality assurance and was well-tolerated in all patients. 98% of pts had good to excellent cosmesis at 12 months with minimal acute toxicity on formal review of digital photographs. All but one patient is without clinical or radiographic evidence of disease at a median follow-up of 19 months. There has been minimal significant late toxicity.

### **Study Rationale**

Can an acceptable outcome be achieved with radiation delivered only to the region of the tumor bed? If this were so, partial breast irradiation may lend itself to much shorter treatment times (one week) as the toxicities to adjacent normal structures (i.e., heart, lung, chest wall, skin, and contralateral breast) should be significantly reduced with this approach. This significantly shortened treatment time could potentially reduce health care costs, improve the quality of life of many patients undergoing BCT, and just as importantly, extend the conservation option to more women by reducing the inconvenience of radiation therapy. The implications of the presented clinical and pathologic data coupled with favorable early outcomes form the basis of the current study.

Patient selection criteria in this protocol have been chosen to minimize the risk of multicentricity and a remote breast recurrence. The key factors are the exclusion of patients with microscopic extension of tumor cells to the inked surgical margins, lobular histologies, tumors larger than 3 cm, and patients having an extensive intraductal component. Patients with involvement of 4 or more axillary lymph nodes have a significant risk for regional nodal relapse, and most radiation oncologists choose to include them in external beam portals. These patients would lose the logistical advantage of a shortened breast treatment regimen. Even with these strict selection criteria, approximately 71,000 women per year in the United States would be candidates for this protocol.

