## **2.2 Secondary Objectives**

- To determine if brachytherapy will have non-inferior toxicity to external beam radiotherapy (5%) at 3 years. Grade 3 or higher toxicity will be scored.
- To evaluate cosmesis at each follow-up by utilizing a cosmesis score based on established Harvard criteria.
- To assess patient satisfaction with breast brachytherapy by a questionnaire pre-brachytherapy, at completion, and post-brachytherapy.
- To perform a dosimetric comparison with an external beam plan for each patient. The following parameters will be evaluated: skin dose, target coverage, dose homogeneity index, and NTDmeans from dose volume histograms for each individual patient for heart, lung, and contralateral breast.
- To assess the ability to interpret mammography after interstitial brachytherapy.
- To evaluate Disease-free, Mastectomy-free, and Overall Survival.

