##### **5.2 Target Volume Definition**

Radioactive implants following lumpectomy are intended to deliver a tumoricidal dose to the target volume. The delineation of this target volume is essential for prescribing a dose and dose distribution capable of sterilizing occult tumor foci in the breast tissue surrounding the excision cavity. The target can be defined either by surgical clips visualized on stereotactic digital mammography, ultrasound, or CT visualization of the post-surgical seroma with subsequent Omnipaque nonionic contrast injection. The target volume will be defined as the volume encompassed by an irregularly-shaped surface 1.5-2 cm outside the excision cavity in all dimensions unless limited by skin or chest wall.

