### **5.6 Dosimetric Characteristics**

- Dose optimization will be guided by dose homogeneity index (DHI) which is defined as  $DHI = (V_{100}-V_{150})/V_{100}$ , where  $V_{100}$  and  $V_{150}$  are the volumes covered by the 100% and 150% isodose lines, respectively. The DHI must be between 0.7-1.0.
- The dose must be prescribed to a depth of  $\geq 5$  mm from the skin surface.
- The following dosimetric parameters must be recorded on the dosimetry form: (1) target volume, (2) seroma volume, (3) percent target covered by chosen isodose line, (4) # of catheters, (5) volume of implant, and (6)  $V_{100}$  and  $V_{150}$ , (7) DHI, and (8) NTDmeans of heart, lung, and contralateral breast from DVH analysis.

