### **10.1.5 Dosimetric analysis**

Dosimetric analysis will be performed and compared to an external beam plan for each patient. The NTDmeans from dose volume histogram analysis for each individual patient for skin, heart, lung, and contralateral breast will be determined.

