 -  DAYS ELAPSED TIME B/N CATHETER PLACEMENT AND START OF BRACHYTHERAPY	 -  Gy HDR PRESCRIPTION DOSE	 -  5 OTHER _____	
 -  TOTAL # OF FRACTIONS	 -  WERE PHOTOGRAPHS TAKEN OF THE BREAST WITH CATHETERS IN PLACE?		
 -  TOTAL # OF FRACTIONS	 -  ITDmean OF THE HEART	 -  ITDmean OF THE LUNG	
 -  TOTAL # OF FRACTIONS	 -  ITDmean OF THE CONTRALATERAL BREAST	 -  THE CLOSEST DISTANCE B/N THE 100% ISODOSE LINE AND THE SKIN

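### The dosimetric comparison with external beam omits the chest wall and has no consistent skin measure; the one skin metric it defines, a mean, can exaggerate sparing next to the implant

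*Combined protocol and SAP*

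**What the plan says.** The Study Rationale names five structures and expects that "the toxicities to adjacent normal structures (i.e., heart, lung, chest wall, skin, and contralateral breast) should be significantly reduced with this approach".

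Four places define or record the dosimetric comparison:

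- **2.2 Secondary Objectives** plans a comparison with an external beam plan for each patient on "skin dose, target coverage, dose homogeneity index, and NTDmeans from dose volume histograms for each individual patient for heart, lung, and contralateral breast". Skin dose stands apart from the NTDmeans and has no metric.
- **5.6 Dosimetric Characteristics**, item (8) of the required recording list, asks for "NTDmeans of heart, lung, and contralateral breast from DVH analysis". It includes no skin dose. The same section requires prescription to a depth of at least 5 mm from the skin surface.
- **10.1.5 Dosimetric analysis** states: "The NTDmeans from dose volume histogram analysis for each individual patient for skin, heart, lung, and contralateral breast will be determined".
- **The Appendix III dosimetry form** has mean fields for heart, lung and contralateral breast (the last reads "ITDmean OF THE CONTRALATERAL BREAST"). For skin it has only the closest distance to the 100% isodose line.

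Section 5.2 extends the target 1.5-2 cm beyond the cavity "in all dimensions unless limited by skin or chest wall". Section 10.2 plans summary statistics for the dosimetric measures. The Appendix IV late scale and the follow-up form grade skin and subcutaneous tissue; neither has a chest-wall or rib item.

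**The concern.** Skin and chest wall are the two structures that 5.2 says can bound the target, so they are where normal tissue lies closest to the prescription volume. One of them is not compared at all. For the other, the only metric defined is an average.

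Heart, lung and contralateral breast lie further from the implant, and a mean dose is a reasonable summary for them. A mean over skin blends a small patch above the implant with a large area that receives little dose. The late skin harms in Appendix IV, such as gross telangiectasia and ulceration, can be local.

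At stake is what the dosimetric objective can conclude. As planned, it cannot address the rationale's expectation for the chest wall, and its skin result could look far more favourable than the dose next to the implant warrants. There is also a practical gap: 10.1.5 needs a skin NTDmean, but neither the 5.6 list nor the form has a field for it.

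**Working it through.** The plan states no figure on this point, so there is none to reproduce. The check has two parts.

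**1. Structures side by side**

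| Place | Chest wall | Skin | Heart, lung, contralateral breast |
|---|---|---|---|
| Study Rationale | named | named | named |
| 2.2 | absent | dose, no metric | NTDmean |
| 5.6 item (8) | absent | absent | NTDmean |
| 10.1.5 | absent | NTDmean | NTDmean |
| Dosimetry form | absent | distance only | mean |

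The chest wall is in 0 of the 4 places that define or record the comparison. Skin is treated in four different ways.

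**2. How far a mean and a near-maximum can diverge (illustration)**

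From the documents: 34 Gy in 10 fractions of 3.4 Gy or 32 Gy in 8 fractions of 4.0 Gy (5.5); whole-breast 45-50 Gy plus a 10-15 Gy boost (1.0 Background).

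Assumed: alpha/beta = 3 Gy; comparator 50 Gy in 25 fractions without boost; the skin dose distributions below.

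Formula: NTD = D(d + 3)/(2 + 3).

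*Isodose lines*
- 100%: 34 × 6.4/5 = 43.5 Gy; 32 × 7/5 = 44.8 Gy.
- 150%: 51 × 8.1/5 = 82.6 Gy; 48 × 9/5 = 86.4 Gy.

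*Near-maximum, skin at 70-100% of prescription in both plans*
- External beam: 50 Gy at 100%; 35 × 4.4/5 = 30.8 Gy at 70%.
- 34 Gy schedule: 43.5 Gy at 100%; 23.8 × 5.38/5 = 25.6 Gy at 70%. Ratios 43.5/50 = 0.87 and 25.6/30.8 = 0.83, a reduction of 13-17%.
- 32 Gy schedule: 44.8/50 = 0.90 and 26.0/30.8 = 0.84, a reduction of 10-16%.

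*Mean, 34 Gy schedule: 2-10% of breast skin at 80-100% of prescription, 20% at 30%, the rest at 5%*
- NTD is 31.1 Gy at 80%, 8.2 Gy at 30% and 1.08 Gy at 5%.
- Low: 0.02 × 31.1 + 0.20 × 8.2 + 0.78 × 1.08 = 3.1 Gy.
- High: 0.10 × 43.5 + 0.20 × 8.2 + 0.70 × 1.08 = 6.7 Gy (6.8 Gy with the 32 Gy schedule).
- Against an assumed external beam skin mean of 30.8 Gy: 1 - 3.1/30.8 = 90% and 1 - 6.7/30.8 = 78%. Against 50 Gy: 94% and 87%. The apparent reduction is therefore roughly 80-90%.

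*Can a mean conceal a local excess?* Suppose 5% of the skin is at 120% of prescription (57.8 Gy) and 95% at 20% (5.0 Gy). The mean is 0.05 × 57.8 + 0.95 × 5.0 = 7.6 Gy. The patch exceeds 50 Gy and the mean gives no sign of it.

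*Sensitivity to the comparator.* Implant NTD passes 50 Gy at 107-109% of prescription (102-113% for alpha/beta of 2 to 4 Gy). If the tissue also received the boost, 55-65 Gy in assumed 2 Gy fractions, the crossing moves to 114-129%. At the 100% line the 34 Gy schedule then gives 43.5/55 = 0.79 to 43.5/65 = 0.67, a reduction of 21-33%.

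*Does the plan limit hot regions?* A homogeneity index of at least 0.7 means V150/V100 ≤ 0.3. Up to 30% of V100 may be on or above the 150% line, and the index does not say where.

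**The case against.** The strongest reply is that the plan never says skin is judged by a mean alone. Section 2.2 lists skin dose as its own parameter, 5.6 sets a minimum prescription depth, and the form records a local measure, the distance from the 100% isodose line to skin. This stands in part: the firmer skin defect is an undefined metric and lists that disagree. A distance is not a dose, however, and cannot be set against an external beam plan.

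A reader might go further and infer that the comparison hides places where the implant is worse. The documents do not support that. They report no skin or chest-wall dose and nothing that places either structure on the 150% line. The near-maximum illustration still favours the implant, and including the boost favours it more. Skin harm is also captured clinically, through toxicity grades, photographs and the physician cosmesis form.

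A reader might also infer that chest-wall harm could not surface at all. That is too strong. Appendix I has general adverse event reporting that is not limited to listed organs, and the Treatment Toxicity Form named in 9.1 is not reproduced, so its fields are unknown. What remains is that no chest-wall item appears in the graded scale or the follow-up form.

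Finally, the rationale is a hedged background statement about toxicity, the endpoint is descriptive, and the near-maximum measure is one choice among several. All true; these points limit the weight of the finding without closing the gap.

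**Conclusion.** The point holds as a gap in coverage and consistency. The chest wall is named in the rationale and bounds the target, yet is absent from all four places that define or record the comparison. Skin has no agreed metric, and the one that 10.1.5 names has no field to feed it.

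A skin mean can overstate sparing near the implant by a wide margin: about 80-90% by mean against 13-17% by near-maximum (10-16% with the 32 Gy schedule). These sizes are illustrative. They rest on alpha/beta of 3 Gy, assumed skin fractions, an assumed external beam skin mean and a 50 Gy comparator without boost. A real disadvantage at skin or chest wall is possible but not shown.

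This is a worthwhile, inexpensive improvement to a descriptive secondary endpoint. The primary endpoint, sample size and treatment rules are unaffected.

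**What to change.** 1. Use one structure list in 2.2, 5.6 item (8), 10.1.5 and the dosimetry form, with one defined set of metrics per structure.
2. Add the chest wall to that list.
3. Add skin dose fields to 5.6 and the form, and define the skin region over which the mean is taken.
4. For skin and chest wall, report a near-maximum dose (for example NTD to the hottest 1 cm³) beside the NTDmean for both plans, and summarise both as within-patient paired differences.
5. State whether the external beam plan includes the boost, and give the alpha/beta used for NTD.

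The cost is a chest-wall contour, possibly a skin contour, and a few more dose volume histogram readings for two plans in each of about 300 patients. The planning CTs exist already, so no extra scan, visit or patient is needed, and no dose or treatment rule changes.
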